# **CARILION CLINIC INSTITUTIONAL REVIEW BOARD**

## **IRB RESEARCH APPLICATION INSTRUCTIONS**

**NOTE: This is a protected document!**

**All responses will now appear as originally formatted and can be adjusted.**

This application is for use by researchers proposing to conduct human subjects research at Carilion Clinic, including the Jefferson College of Health Sciences, or who will use Carilion services as part of the research process. The application is for use by the Carilion Institutional Review Board, a committee charged with protecting the rights and welfare of human subjects in research. The entire application must be completed if the proposed research involves Carilion faculty, employees, students, facilities or patients.

Research protocols may be reviewed at convened meetings of the IRB or through a single reviewer process involving the IRB chair and staff. The type of review is determined by the nature of the project, the level of potential risk to research subjects and the characteristics of the subject population. The final determination of the type of review applicable to a study is made by the IRB.

- **Full Board Reviews:** Research that would require review at a convened meeting of the IRB would include but is not limited to research that involves: 1)more than minimal risk, 2)vulnerable populations, 3)experimental drugs or devices 4)invasive procedures, or 5)deception (e.g., in behavioral research). A schedule of IRB meetings can be found on the Carilion IRB website.
- **Expedited or Exempt Reviews:** Some studies may not require review by the convened IRB, but may be eligible for "Expedited review" or "Exempt status" after review by one or more IRB members. Expedited studies involve no more than minimal risk to subjects. Federal regulations define minimal risk as the probability that the magnitude of harm or discomfort anticipated in the research are not greater in of themselves than those ordinarily encountered in daily life or during the performance of routine physical or psychological examinations or tests. Some research may be Exempt from further review once this initial determination is made. The Carilion IRB must determine whether proposed studies meet the criteria for Expedited or Exempt review.

**All research team members must complete Carilion IRB education requirements before research can be approved.** Further information regarding education requirements can be found on the Carilion IRB web site: <http://www.carilionclinic.org/Carilion/IRB>.

1. Has the Principal Investigator ever had any research suspended or terminated by an IRB?  
 Yes       No
  - If yes, please explain:
2. Has any version of this research protocol ever been submitted to any other IRB?  
 Yes       No
  - If yes, please attach a copy of all IRB correspondence
3. Has the Principal Investigator ever been convicted of a crime, disciplined by a public or private medical organization, disciplined by a licensing authority or is the Principal Investigator currently the subject of such a proceeding?  
 Yes       No
  - If yes, please explain:
4. Have any of the other investigators or study team members ever been convicted of a crime, disciplined by a public or private medical organization, disciplined by a licensing authority, or are any currently the subject of such a proceeding?  
 Yes       No
  - If yes, please explain:
5. **Location of Research:**
  - Check the facility where research activities will take place (please check all that apply):

 CRMH	 CNRVMC	 JCHS	 CC Physician's Office
 CRCH	 CFMH	 CRMH Rehab	 Other: Carilion Institute of Orthopedics and Neurosciences (ION)
  - List all departments within the facility where research activities will take place: Carilion Orthopedics
6. **Collaboration:**
  - Will this research involve collaboration with another institution?  Yes       No
  - If yes, name the institution:
7. **Sponsor:**
  - Will this research be sponsored by an institution outside of Carilion?  Yes       No
  - If yes, name the institution:
8. **Funding Source** (check only one):
  - Carilion RAP grant
  - Federal/state agency (specify):
  - Other grant (specify):
  - Industry/commercial (specify):
  - Private, non-profit (specify):
  - No funding; equipment, supplies, and/or services will be provided (specify company):
  - No funding; no equipment, supplies, and/or services will be provided
  - Other (specify):
9. Anticipated Start Date: October 1st, 2017
10. Estimated Time Needed to Complete Study: September 30, 2018

## SECTION II: DRUG, DEVICE AND BIOLOGIC STUDIES ONLY

N/A

11. What is the name(s) of the drug, device or biologic that will be used in this study:
12. Please attach documentation to confirm FDA approval of this drug, device or biologic. Check one below:
  - Package Insert
  - Printed Information from the FDA website confirming FDA approval
  - Letter from FDA granting approval
  - Not available; FDA has not approved

13. Does the research study involve an Investigational New Drug (IND) or Biologic? An IND number is required if a drug or biologic is used in a manner outside the labeling approved by the FDA.

Yes  No

- If yes, please provide the IND number assigned by the FDA. If an IND number is not available please explain why an IND was not obtained. If you believe the drug is exempt from IND approval, please submit an IND Determination form that can be found on the IRB web site. Note: Investigators may be asked to have an IND determination application submitted to the FDA.

14. Does the research involve a device that is being used outside the labeling approved by the FDA?

Yes  No

If yes:

- Please provide the Investigation Device Exemption (IDE) number provided by the FDA:
- Attach one of the following:
  - FDA letter granting an IDE
  - A letter from the sponsor or investigator/sponsor stating the study device is non-significant risk
  - A letter explaining why the investigation is exempt from IDE requirements

### SECTION III: STUDY PROTOCOL

15. **Study Abstract:** Provide a brief, non-technical summary of the study, including study purpose and methods.

The purpose of this study is to quantify the impact of a formalized pain management education program on the outcome and experience of patients undergoing outpatient, upper extremity, orthopedic surgery. Outcome measures include the validated Quality of Recovery-15 patient survey and PROMIS survey (selected short forms evaluating pain and medication side effects), as well as measures of patient behavior (amount of pain medication used, number of calls/visits to a medical provider for pain-related concerns), pain levels (1-10 scale), reported side effects, and patient knowledge as measured on a follow-up questionnaire. It is the premise of this study that patient education regarding perioperative pain management could benefit patients in several ways:

- 1) empowering patients to make informed decisions regarding the pain medications and modalities they choose,
- 2) reducing the incidence and severity of pain medication related side effects or complications,
- 3) improving post-operative pain control,
- 4) improving patient satisfaction, and
- 5) reducing the use of narcotic.

Four hundred (400) adult patients undergoing elective outpatient, upper extremity, orthopedic surgeries will be recruited by the surgeon-investigators. Patients will be randomized to view one of two educational programs: 1) a 2-video series regarding post-operative pain management or 2) a video regarding wound care and activity. Randomization will be stratified based on initial narcotic prescription size, which has been shown to influence narcotic use, and baseline pain medication use.

These patients will be encouraged to review the video online in the week before surgery. An intake enrollment form will be completed by an investigator using demographic information available in the chart.

Participants in both arms will complete their Patient Education Study Diary daily, for 7 days following their surgery. There are two versions of this diary: the Wound Education Version asks patients to report daily pain medication use. The Pain Education Version does not include this section as patients in the pain management arm of the study record this information in their Recovery Diary.

 The guidelines have been developed in conjunction with the upper extremity surgeons to reflect their current practice. The purpose of the guidelines is to reduce inadvertent variability, particularly when residents and other providers provide the post-operative prescription. Despite the guideline, the surgeon is still encouraged to provide the pain medication prescription he/she feels is most appropriate for the patient.

The Patient Education Study Diary includes a daily pain scale, the QoR-15 on day 2, the selected PROMIS short forms on day 3 and knowledge quiz on day 7. It also contains opportunity to report dressing changes, co-analgesic modalities (ice, elevation, etc), and possible medication side effects. There are daily questions regarding confidence, feeling in control, and satisfaction. The final day also has questions regarding how many times the videos were viewed, the number of contacts with a healthcare provider for pain and wound related issues, and concurrent use of other sedating substances (sleeping pills, alcohol, street drugs, other sedating medications). Patients in the control group (wound care) will also record all pain medications used each day along with any side effects of said medications. Participants in the intervention (pain management) group will record their pain medication use in the additional Recovery Medication Diary provided. The patient will return the diary at the first post-operative visit or by mail.

Patients may be contacted by phone within 7-10 days after the appointment if study materials are not complete. Information regarding the initial narcotic prescription, CPT procedure codes, concurrent NSAID prescription, and type of anaesthetic will be obtained from EPIC by chart review.

The patient will be contacted again by phone and/or mail 1 year after surgery (12-14 months) using the contact information available in EPIC to determine the self-reported prevalence of chronic pain and pain medication use (yes or no answers):

1. Do you have pain on a daily or weekly basis?
2. In the past year, have you taken prescription opioid (or narcotic) pain medication most days or most weeks?
3. In the past year, have any other pain medications (prescription or over the counter) most days or most weeks?

Measured outcomes will include: QoR-15 and PROMIS scores, number of narcotic pills used in the first week after surgery, daily pain level (by 0-10 rating scale), patient-reported satisfaction and feeling of control, related calls/visits to a health care providers, use of non-narcotic adjunct pain relief modalities, incidence of side effects and adverse events, demonstrated patient knowledge as measured by score on the follow-up quiz, and prevalence of chronic pain, long term narcotic and non-narcotic pain medication use. Positive improvements in some or all of these measurements are expected with this patient education intervention.

16. **Background:** Summarize background information about the research question(s.) Tell why the research is needed and include the relevance of this research to the contribution of this field of study. Also, provide references to relevant articles in the literature. (If you have more than 10 references, please submit the list of references as a separate attachment. Otherwise, please insert them here.)

Pain after surgery is a common experience and is not always well controlled. Results from a recent five-year survey of adult surgical patients (N = 300) showed ~86% experienced pain after surgery; of these, 75% had moderate/extreme pain during the immediate post-surgical period, with 74% still experiencing these levels of pain after discharge. Post-surgical pain was the most prominent pre-surgical patient concern, and nearly half reported they had high/very high anxiety levels about pain before surgery.

In the case of outpatient orthopedic surgery at Carilion, there are no guidelines or standardized practice for pre-operative education of the patient regarding post-operative pain control. The majority of teaching regarding pain management is usually undertaken by the discharge nurse shortly after the patient has emerged from anesthetic at a time when the patient's ability to retain new knowledge may be compromised. Patients often leave hospital with local anesthetic or a block controlling their pain, only to experience a higher level of pain some hours later. Patients then generally have the option of several medication choices (acetaminophen, narcotic or narcotic-combination medications, and non-steroidal anti-inflammatories) with which to essentially self-medicate at home, in combination with non-pharmaceutical modalities. Some patients are also regular users of central nervous system depressors, such as muscle relaxants, sleeping pills, anti-depressants, and alcohol, which may contribute to risk of serious complications.

The importance of patient education regarding peri-operative pain control is agreed upon, although support in the literature, especially in the outpatient setting, is not strong. In 2016, a clinical guideline for the

management of post-operative pain was published jointly by American Pain Society, the American Society of Regional Anesthesia and Pain Medicine, and the American Society of Anesthesiologists' Committee on Regional Anesthesia, Executive Committee, and Administrative Council. Their recommendations included the following:

"Patients should be counseled on how to take pain medications safely and to manage side effects to optimize pain control and recovery with return to usual activities. This might be particularly important for the growing number of outpatient surgical patients. Patients and families should be informed that the use of other central nervous depressants (including alcohol) or illicit drugs in combination with opioids can result in accidental overdose and death. Discharge teaching should include a discussion of the plan for reduction and discontinuation of opioids as the acute pain resolves, as well as appropriate disposal of unused supplies of opioids and other medications."

Pre-operative education for post-discharge pain control has been promoted by AORN: "Effective communication between the patient, designated support person(s), and perioperative team members enhances the patient's capacity for medication self-management after discharge."

Specific communication about pain has been shown to correlate strongly with patient satisfaction. Five dimensions have been identified as impacting on patient satisfaction: information provision; physical comfort/discomfort; emotional support; involvement in care; and privacy. In an inpatient setting, higher self-report of pain was associated with lower levels of satisfaction. Patients reporting adequate teaching rated a higher satisfaction score (4.46) than patients reporting inadequate teaching.

Patient education in the outpatient setting is essential in allowing the active participation of the patient in their own health care, and could reasonably increase patient safety in a way similar to in-hospital programs that have been shown to reduce medication errors. The effect of pre-operative patient education on decreasing narcotic use and improving pain control has been demonstrated on one study of 135 patients who were randomized to receive educational intervention vs no education.

Recent interest in the over-prescription of narcotic pain medication after outpatient surgery has led to several studies which suggest standardized protocols for prescription sizes. The Hand Section of the Department of Orthopedics at Carilion clinic has recently submitted for publication a manuscript showing the effect of initial prescription size on narcotic use in this setting. We are also participating in a multi-center international trial of narcotic vs. non-narcotic analgesics for pain control after carpal tunnel surgery. Investigating the role of patient education in post-operative pain management is an extension of this line of research.

This study will be a prospective, randomized, placebo-controlled experimental study investigating the effect of a formalized patient education program (videos and recovery diary handout) on patient experience and outcome after outpatient orthopedic upper extremity surgery, using both validated and non-validated outcome measures.

17. **Objectives:** State the research hypothesis or the question that the research will answer. List the research objectives and expected outcomes. **A primary outcome or objective must be identified.** After the statement of the primary objective, secondary objectives may be listed. Objectives should be simple and specific.

Hypothesis: Patient experience and outcome after outpatient upper extremity orthopedic surgery can be improved by a formalized education program (video and handout) regarding post-operative pain management.

Primary outcome:

1. QoR-15 scores (post-operative day "POD" 2),
  - a. 15-question validated outcome measurement tool used in the setting of outpatient surgery which takes about 2.5 minutes to complete and includes pain as one of its outcome domains

Secondary Outcomes:

2. PROMIS short forms administered on POD 3 – (GI belly pain 5a, GI nausea and vomiting 4a, Pain Intensity 3a, Pain Interference 4a, Sleep Disturbance 4a, Cognitive Function 4a)
3. number of narcotic pills used – 7 days,
4. daily pain level (by 0-10 rating scale) – 7 days,
5. patient-reported satisfaction and feeling of control (4 point rating scale)
6. number of pain-related calls/visits to a healthcare provider
7. use of non-narcotic adjunct pain relief medication and modalities
8. incidence of high risk activities (combining narcotics with muscle relaxants/sedatives/alcohol, etc.; combining prn NSAIDs with regularly dosed prescription NSAIDs, exceeding daily recommended doses)
9. incidence of side effects and adverse events,
10. demonstrated patient knowledge as measured by score on the follow-up quiz, and
11. prevalence of chronic opioid use.

Positive improvements in some or all of these measurements are expected with this patient education intervention. The Quality of Recovery-15 survey is a 15-question validated outcome measurement tool used in the setting of outpatient surgery which takes about 2.5 minutes to complete and includes pain as one of its outcome domains

18. **Study Design:** Give a description of the research design including use of placebo, randomization and an explanation of what is experimental. Include type of study: descriptive, retrospective, cross-sectional, longitudinal, prospective observational, pilot, experimental (controlled or non-controlled) or pilot.

A prospective, randomized, controlled study. The experimental intervention is exposure of the subject to a standardized educational program on post-operative pain management, while the control is exposure to a standardized educational program on wound care.

19. **Study Population:** Describe the subject population, including age, gender, ethnic characteristics and health status. State the inclusion/exclusion criteria along with how this was determined, and by whom. Please state whether pregnant women, children, or other vulnerable groups will be included or excluded. Provide rationale for using or excluding special populations. State the number of subjects or subject records necessary to complete the research.

400 patients undergoing outpatient, upper extremity, orthopedic surgery meeting the following inclusion and exclusion criteria will be recruited.

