The surgeon will inform the designated enrollment investigator (verbally) of the anticipated prescription class for use in randomization. The designated enrollment investigator will send the surgeon a staff message in EPIC to document that number for reference on the day of surgery.

Patients who agree to participate in the study will sign the consent form. The designated enrollment investigator will keep track of all patients who are consented for surgery but do not enroll in the study, collecting only the number of such patients and their reason for not entering the study (patient declines or which eligibility criterion is not met). No identifying data or other demographic data will be collected from patients who do not consent to enter the study. This information will be recorded in REDCap.

2. Randomization - < 1 minute

They will then be randomized to a study group using a REDCap stratified randomization protocol.

Randomization will be stratified by anticipated post-operative prescription (none, tramadol, 10 narcotic pills, 20 narcotic pills, 30 narcotic pills, >30 narcotic pills). Other factors that will be controlled for through randomization include:

1)

The surgeon and other treating providers will be blinded as to the randomization of the patient. In some cases, the patient may initiate a discussion with the surgeon which necessarily reveals the randomization – this is necessary to avoid interference with physician-patient communication (avoiding negatively impacting patient care) and will be considered acceptable for this study.

3. Data collection – enrollment phase – 10 minutes

An enrollment form is completed by the designated enrollment investigator based on patient interview and/or chart review at the time of enrollment.

At the pre-operative visit prior to video viewing, patients will complete, using REDCap online with the assistance of an investigator, the following:

- I. Quality of Recovery 15 (2.5 minutes)
- II. PROMIS short forms in the following domains: (approximately 6 minutes)
  - a. Physical Health – Gastrointestinal - Belly Pain 5a
  - b. Physical Health – Gastrointestinal – Nausea and Vomiting 4a
  - c. Mental Health – Cognitive Function 4a
  - d. Sleep Disturbance 4a
  - e. Pain Intensity 3a
  - f. Pain Interference 4a
- 4. Educational Intervention (experimental): (6-12 minute video, depending on randomization)
  - 1) Pain Management Education (Intervention)

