**Patient Demographic Data:**

Name

EMPI

CSN

MRN

Contact phone number

Age

Gender

Pre-existing pain medication use (opioids, acetaminophen, NSAIDS, Lyrica, Neurontin)

Patient race, ethnicity, education level

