**Outcome Measure Data:**

1. QoR-15 scores (primary outcome),
2. Selected short form PROMIS questionnaires,
3. number of narcotic pills used,
4. daily pain level (by 0-10 rating scale) for days 0-7,
5. patient-reported satisfaction and feeling of control (10 point rating scale),
6. calls/visits to a health care provider for pain or related concerns
7. use of non-narcotic adjunct pain relief medications and modalities,
8. incidence of side effects and adverse events
9. reported frequency of noting pain medication dose times,
10. demonstrated patient knowledge as measured by score on the follow-up quiz, and prevalence of chronic pain, long term narcotic and non-narcotic pain medication use.

Data will be collected by chart review (for demographic data and data pertaining to the surgery, anaesthetic, and initial narcotic prescription), physician and patient reporting, and by patient diary/surveys (which will be completed by the patient at home and returned at the follow-up visit or by mail). Follow-up phone calls will act as a reminder to help encourage completion of the study. Information regarding how many times a video was viewed will be collected by patient questionnaire (measured outcome to be used in analysis), reviewing Mychart data, and counting Youtube hits.

22. **Statistical Analysis:** State how qualitative and/or quantitative data will be analyzed. This must include a statement from a statistician that there is sufficient power to determine the primary study outcome or objective. Other outcomes may be listed as secondary and descriptive. If this is a proof of concept or feasibility study that includes limited efficacy testing, there must be a statistician statement that the appropriate design is in place to determine whether an intervention should be recommended for broader efficacy testing. If a study is meant to be solely descriptive, then results apply only to the sample being studied and conclusions cannot be drawn about the larger population; therefore, the primary outcome or objective must be limited in scope.

Standard descriptive statistics will be undertaken. All data will be integrated into a mixed model ANOVA with appropriate post-hoc comparisons by group as appropriate. Analysis will be carried out with the assistance of a qualified biostatistician.

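### The abstract names two stratification factors, but the randomisation step gives levels and a supply route for only one, so the protocol does not fix a single allocation scheme

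*Protocol*

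**What the plan says.** The protocol describes stratification in two places.

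- **Item 15, Study Abstract:** "Randomization will be stratified based on initial narcotic prescription size, which has been shown to influence narcotic use, and baseline pain medication use". This names two factors and gives no levels for either.
- **Item 20, Methodology, step 2 (Randomization):** "Randomization will be stratified by anticipated post-operative prescription (none, tramadol, 10 narcotic pills, 20 narcotic pills, 30 narcotic pills, >30 narcotic pills". This is one factor with six levels. The text continues "Other factors that will be controlled for through randomization include", followed by an item 1) that is empty in the text at hand.

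Three other places bear on how the scheme would run.

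- **Item 20, step 1:** "The surgeon will inform the designated enrollment investigator (verbally) of the anticipated prescription class for use in randomization". No other information is described as being supplied for that purpose.
- **Item 20, step 3, listed after randomisation:** "An enrollment form is completed by the designated enrollment investigator based on patient interview and/or chart review at the time of enrollment".
- **Item 21, Patient Demographic Data:** "Pre-existing pain medication use (opioids, acetaminophen, NSAIDS, Lyrica, Neurontin" is collected as a baseline variable. It is not labelled a stratum, and nothing says how the five drug types would be turned into one.

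On analysis, item 22 says "All data will be integrated into a mixed model ANOVA". Item 20, step 7 adds an analysis of age, gender, and surgery and medication related variables. Neither ties the model to the randomisation factors.

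**The concern.** REDCap needs one fixed list of factors and levels before the first patient is allocated, and for this investigator-initiated study the application itself serves as the protocol. Someone building the randomisation from the abstract would set up two factors. Someone building it from the Methodology text at hand could set up only one. In the second case a variable that the abstract promises to balance is left to chance.

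The unsettled list also carries into the analysis. A model that reflects the randomisation cannot be written until the factors are known. If strata are used but then ignored, the usual standard error for the arm difference is too large.

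**Working it through.** **1. The two descriptions side by side**

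| Element | Study Abstract (item 15) | Methodology (item 20) |
|---|---|---|
| Prescription factor | Initial narcotic prescription size, no levels | Anticipated prescription, six levels |
| Baseline pain medication use | Named as a factor, no levels | Not named in the text at hand; the list of other factors is blank |
| Supplied for randomisation | Not described | Prescription class only |
| Enrolment form | Not ordered relative to randomisation | Step 3, after randomisation (step 2) |

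Even if the blank item named baseline medication use, the steps as written do not describe obtaining it before allocation.

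**2. Size of the strata.** With 400 patients (item 19), six strata average 400/6 ≈ 67 patients. A yes/no split of baseline medication use is an assumption, since the protocol gives no levels. It would make 6 × 2 = 12 strata, averaging 400/12 ≈ 33. Either is workable.

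**3. The plan's own sample size.** Item 22 gives a difference of 8, SD 25, α = 0.05 and power 0.8. With a two-sided test:

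- n per group = 2(1.960 + 0.842)² × 25² / 8² = 153.3, so 154, as stated.
- With 20% attrition, 154/0.8 = 192.5, so 193, which the plan rounds up to 200.

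The figure reproduces and does not depend on the stratification list.

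**4. What ignoring the strata would cost.** Let R² be the share of QoR-15 variance that the strata explain. The documents give no value, so 5%, 10% and 20% are assumed. The normal approximation is used at 154 per group.

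- Usual standard error: 25 × √(2/154) = 2.849. The standardised difference is 8/2.849 = 2.808.
- Stratified allocation already reduces the true standard error by √(1 − R²), but an unadjusted analysis still reports 2.849. The overstatement is 1/√(1 − R²).
- Power of the unadjusted test after stratified allocation: Φ((2.808 − 1.960)/√(1 − R²)).
- Power of the adjusted test: Φ(2.808/√(1 − R²) − 1.960).
- True two-sided type I error of the unadjusted test: 2Φ(−1.960/√(1 − R²)).

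| R² (assumed) | SE overstated by | Power, strata ignored | Power, strata modelled | Gain in points | Type I error, strata ignored |
|---|---|---|---|---|---|
| 5% | 2.6% | 80.8% | 82.1% | 1.4 | 4.4% |
| 10% | 5.4% | 81.4% | 84.1% | 2.7 | 3.9% |
| 20% | 11.8% | 82.8% | 88.1% | 5.2 | 2.8% |

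Gains are computed before rounding. The right comparator is the unadjusted test after stratified allocation. Using the power of a design without stratification (about 80%) would credit adjustment with part of the precision that the stratified allocation already provides.

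**The case against.** The strongest reply is that the two sections can be compatible. Methodology announces further factors controlled through randomisation, and the abstract names one. If the empty item is text lost in reading the PDF, it may have named exactly this factor, and lost text is not an error in the plan. This stands to the extent that a reader might infer that the methods stratify by prescription alone, and the documents do not support that reading. It does not supply levels for the factor, and it leaves the order of the steps, in which only the prescription class is supplied before allocation.

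A reader might also infer that the abstract stratifies on the prescription actually issued, because it says initial where Methodology says anticipated. The abstract is a non-technical summary, and Methodology is clear that the surgeon states the anticipated class beforehand. The difference is loose wording that the operative text resolves. It is still worth aligning, because the abstract also uses the term initial narcotic prescription for what is later taken from the chart, and a footnote there leaves the surgeon free to prescribe otherwise.

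A third tempting reading is that the protocol errs by not listing the strata as model terms. That detail commonly sits in a statistical analysis plan, and none is shown here, so its absence is no fault. The modelling advice is an improvement that depends on settling the list.

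Finally, leaving one baseline variable to chance with 200 patients per arm does not bias the comparison, and the variable is collected anyway. This is correct and limits the weight of the point.

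**Conclusion.** The point holds in limited form. The abstract commits to stratifying by baseline pain medication use. The operative text at hand gives that factor no levels, describes no step that supplies it before allocation, and leaves the list where it might appear blank. The allocation procedure therefore cannot be reproduced from the protocol as written.

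The consequence is modest. The sample size stands, no bias arises, and ignoring the strata would err on the conservative side. Modelling them is worth about 1 to 5 points of power at 154 per group. That range rests on the assumed 5% to 20% of variance explained, balanced strata and the normal approximation. This should be corrected, but it does not invalidate the design.

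**What to change.** - State one list of stratification factors, with levels, identically in items 15 and 20. Use anticipated prescription class throughout, and keep the prescription actually issued as a separate variable.
- If baseline pain medication use is kept, give its levels (the sponsor's choice), complete the blank item, and record the variable before allocation. If it is not kept, remove it from the abstract and delete the blank item or fill it with whatever else was meant.
- Include the factors as recorded at randomisation, not the prescription issued, in the primary QoR-15 model, here or in the statistical analysis plan.

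The cost is protocol wording, a REDCap setting and possibly a small reordering of the enrolment steps so that baseline medication use is known before allocation. Both variables are already obtained for the study, so no new data collection is needed.
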